5.1 Number of Subjects, Duration, and Number of Investigational Devices

This study will involve up to 75 subjects implanted with the study device among all active sites. As not all patients consented for evaluation will go forward to implantation, the number of subjects consented for the study is expected to be higher (up to 150). No site will implant more than 15 subjects without prior authorization from Medtronic in order to minimize bias.

Subjects will be consented for follow-up through five years following implantation, and all implanted subjects will be followed per protocol through five years following implantation. Subjects who exit from the study after implantation will not be replaced. The enrollment period is estimated to be between 9 and 20 months, and the estimated total study duration (first subject implanted to last subject completing his/her last follow-up exam) is estimated to be seven years.

The number of investigational TAVR systems involved in this study is estimated to be between 75 and 150 (inclusive of devices used during index implantation procedures, devices opened but not used, and devices shipped to sites as inventory for the study but not opened or used).

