6.7 Subject Disposition

Sites will maintain a log of subjects consented, the subject ID numbers assigned to them, and the dates of their implants (or attempted implants). Subjects who are consented but are not taken to the procedure room for implantation should be exited from the study and need not be followed beyond the date of study exit.

Subjects taken to the procedure room for implantation, and any of the following occurred: anesthesia administered, vascular line placed, TEE placed or any monitoring line placed, but do not receive a TAV for any reason should be followed for safety events for 30 days after the procedure or through the hospitalization, whichever is longer, and then exited from the study. Subjects that have their TAV explanted should be followed for safety events for 30 days after the explant procedure, or through resolution of related adverse events, whichever is longer, then exited from the study.

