10.5 Efficacy Endpoints

Efficacy endpoints include:

1. Device success (VARC-2)
2. Cardiovascular and heart failure hospitalizations at 30 days and 6 months
3. Heart failure events at 30 days and 6 months
4. Hemodynamic performance metrics by Doppler echocardiography at discharge, 30 days, and 6 months
 - Mean aortic gradient

- Effective orifice area
 - Degree of total, para, and transvalvular prosthetic regurgitation
 - Incidence of moderate and severe patient-prosthesis mismatch (PPM)
5. Change from baseline in New York Heart Association (NYHA) functional classification at 30 days and 6 months
 6. Change in six-minute walk test (6MWT) from baseline at 6 months
 7. Change in Kansas City Cardiomyopathy (KCCQ) from baseline at 30 days and 6 months
 8. Change in left ventricular ejection fraction (LVEF) from baseline at 6 months
 9. Change in peak global longitudinal strain (GLS) from baseline at 6 months
 10. Change in left ventricular filling pressure (E:e') from baseline at 6 months
 11. Change in stroke volume index (SVI) from baseline at 6 months
 12. Change in NT-pro B-type natriuretic peptide (NT-proBNP) from baseline at 6 months

Analyses of the efficacy endpoints will be descriptive. The attempted implant set will be used for safety and quality of life outcomes. However, the efficacy endpoints involving echocardiographic variables will be analyzed for the implanted set. Continuous variables will be summarized as the number of subjects, mean, standard deviation, median, first and third quartiles, minimums, and maximums. Categorical variables will be summarized as counts and percentages. For each time-related event, Kaplan-Meier rates (cumulative incidence) and 95% two-sided confidence intervals will be calculated. Efficacy endpoints involving echocardiographic variables will be based on ECL reported data.

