7.1.3 Analysis Sets

The enrolled population will consist of all subjects who signed the informed consent. The following analysis sets are defined within the enrolled population:

1. **Attempted Implant set:** The attempted implant data set will include all subjects with an attempted implant procedure, where an attempted implant is defined as when the subject is brought into the procedure room and any of the following have occurred: anesthesia administered, vascular line placed, Transesophageal echocardiography (TEE) placed or any monitoring line placed. Day 0 is the date of first attempted procedure.
2. **Implanted set:** The implanted data set includes all subjects with an attempted implant where the study device is implanted, defined as when the transcatheter aortic valve (TAV) is fully released from the delivery catheter system (DCS). Day 0 is the date of first attempted procedure.

In general, the primary analysis of safety, clinical outcomes, and quality of life (QoL) outcomes will be performed using the Attempted Implant analysis set and primary analysis of echo-related outcomes will be performed using the Implanted analysis set. The primary analysis population for each endpoint are detailed in Section 7.9. Analysis performed using analysis sets other than the primary would be considered supportive.

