7.9.2 Efficacy Endpoints

7.9.2.1 Device success (VARC-2)

Device success is defined as meeting all of the following:

- Absence of procedural mortality, AND
- Correct positioning of a single prosthetic heart valve into the proper anatomical location, AND
- Absence of patient prosthesis-mismatch AND mean aortic valve gradient < 20 mmHg (or peak velocity < 3 m/sec), AND
- Absence of moderate or severe prosthetic valve regurgitation.

Components of device success will be reported on the procedure CRF, the echo core lab CRF at discharge, and CEC CRF:

- Procedural mortality will be defined as any death occurring within 30 days of implant or prior to hospital discharge.
- Correct positioning of the single prosthetic heart valve into the proper anatomical location will be reported by the investigator on the procedure CRF.
- Absence of patient-prosthesis mismatch will be derived from the echo core lab data at discharge. Patient prosthesis mismatch is defined in Section 7.9.2.4.
- Mean aortic valve gradient < 20 mmHg (or peak velocity < 3 m/sec) will be derived from the echo core lab CRF at discharge
- Absence of moderate or severe prosthetic valve regurgitation will be derived from the echo core lab CRF at discharge

The endpoint will be reported as the count and percentage of subjects achieving device success with two-sided 95% exact binomial confidence interval. Subjects will be defined as success if all components are met. Subjects will be defined as failure if any one component with available data is not met, regardless if data are available for all components. Subjects missing data for any components and not meeting criteria for failure will be considered to have a missing outcome. The numerator will include the number of subjects with device success and the denominator will include subjects evaluable for device success (known status of success or failure). The components of device success will also be summarized descriptively. The endpoint will be analyzed using the Implanted set.

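### Device success is planned only among subjects whose valve was fully released, so attempted procedures that end without a released valve drop out of the rate

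*SAP*

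**What the plan says.** SAP 7.9.2.1 defines device success as a composite: no procedural mortality, a single valve correctly positioned, no patient-prosthesis mismatch with an acceptable gradient or velocity, and no moderate or severe regurgitation. Positioning comes from the procedure CRF. Mismatch, gradient or velocity, and regurgitation come from the core-lab echo at discharge. The rate is taken over evaluable subjects with an exact binomial 95% interval. On the analysis set the section says: "The components of device success will also be summarized descriptively. The endpoint will be analyzed using the Implanted set".

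SAP 7.1.3 admits a subject to the Implanted set only once the TAV has been fully released from the delivery catheter. The Attempted Implant set is wider. It starts when the subject is in the procedure room and has received anesthesia, a TEE probe, or a vascular or monitoring line. For both sets "Day 0 is the date of first attempted procedure".

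Protocol 10.5 takes the same line as the SAP: "the efficacy endpoints involving echocardiographic variables will be analyzed for the implanted set". Protocol 6.7 provides for subjects who meet the attempt definition "but do not receive a TAV for any reason should be followed for safety events for 30 days after the procedure" or through the hospitalization if that is longer; they then leave the study.

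Two further SAP statements bear on the point. On incomplete data, 7.9.2.1 says: "Subjects will be defined as failure if any one component with available data is not met, regardless if data are available for all components". On other sets, 7.1.3 says: "Analysis performed using analysis sets other than the primary would be considered supportive". Neither document specifies such a supportive analysis for device success.

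**The concern.** One of the things device success asks is whether the procedure ended with one valve in the right place. A procedure that ends with no valve released has not achieved that, yet the choice of set removes the subject before the question is asked. The omission works in one direction only: it cannot lower the rate, and it raises it whenever such a case occurs and at least one implanted subject succeeds.

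A death before release would also fall outside this rate, although procedural mortality is one of its components. It would still be counted in all-cause mortality, which uses the Attempted Implant set.

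The second primary objective is to estimate event rates for planning pivotal studies. A rate conditional on release and a rate per attempted procedure answer different questions, and a pivotal design needs to know which one it has been given.

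The gap is narrow. A malpositioned valve, a second valve, or a death after release stays in the Implanted set and is counted. So is a subject whose first attempt fails but who later receives a valve.

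**Working it through.** The documents state no expected device success rate, no threshold and no expected number of attempted-but-not-implanted subjects, and the 75 was not derived statistically. There is no planned figure to reproduce, so the check is of size and direction under stated assumptions.

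**Inputs from the documents**
- n = 75 implanted. Protocol 5.1 sets the limit on implanted subjects: "This study will involve up to 75 subjects implanted with the study device among all active sites". Never-released subjects therefore come on top of the 75.
- n = 50 at the low end of the initial analysis (SAP 7.8).
- Interval: exact (Clopper-Pearson) two-sided 95%, as in SAP 7.9.2.1.

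**Assumed**
- p, the success rate among implanted subjects: 80% to 100%.
- k, the number attempted with no valve released: 1 to 3, each counted as a failure.
- All implanted subjects evaluable, except where stated.

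**Difference between the two rates**

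Implanted-set rate = p. Attempted-set rate = pn/(n+k). Difference = p − pn/(n+k) = pk/(n+k), which is zero when k = 0.

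| n | k | p = 80% | p = 100% |
|---|---|---|---|
| 75 | 1 | 0.80×1/76 = 1.05 points | 1/76 = 1.32 points |
| 75 | 2 | 0.80×2/77 = 2.08 | 2/77 = 2.60 |
| 75 | 3 | 0.80×3/78 = 3.08 | 3/78 = 3.85 |
| 50 | 1 | 0.80×1/51 = 1.57 | 1/51 = 1.96 |
| 50 | 3 | 0.80×3/53 = 4.53 | 3/53 = 5.66 |

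**Chance that the issue arises at all**

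If each attempted subject has probability r of never having a valve released, the chance of at least one by the 75th implant is 1 − (1−r)^75, and the expected number is 75r/(1−r).

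| Assumed r | Chance of k ≥ 1 | Expected k |
|---|---|---|
| 0.5% | 31.3% | 0.38 |
| 1% | 52.9% | 0.76 |
| 2% | 78.0% | 1.53 |
| 3% | 89.8% | 2.32 |

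**Worked example (assumed 68 successes among 75 implanted)**

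| Set | Rate | Exact 95% CI |
|---|---|---|
| Implanted | 68/75 = 90.7% | 81.7-96.2 |
| Attempted, k = 1 | 68/76 = 89.5% | 80.3-95.3 |
| Attempted, k = 2 | 68/77 = 88.3% | 79.0-94.5 |
| Attempted, k = 3 | 68/78 = 87.2% | 77.7-93.7 |

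The Implanted-set interval is 96.2 − 81.7 = 14.5 points wide. The attempted-set rate falls below its lower limit of 81.7% only at k = 9: k = 8 gives 68/83 = 81.9%, and k = 9 gives 68/84 = 81.0%.

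**Rebuilding the rate from planned output**

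If the report gives x successes among m evaluable implanted subjects, and disposition gives k as attempted minus implanted, the attempted-set rate is x/(m+k). With 5 missing outcomes and k = 2 (both assumed), a reported 63/70 = 90.0% (80.5-95.9) becomes 63/72 = 87.5% (77.6-94.1).

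**The case against.** The strongest reply is that this is a disclosed choice that follows the protocol. Three of the component measures come from discharge echo, protocol 10.5 sends such endpoints to the implanted set, and the SAP complies. That is correct, and there is no conflict to repair.

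The information is also largely planned already. SAP 7.1.1 tabulates attempted and implanted counts. SAP 7.7 summarizes procedure data in the Attempted Implant set, and protocol 13.7 collects valve position and use of more than one valve. Mortality is analyzed in the attempted set. A reader can rebuild the point estimate and, with the right software, its interval. This stands, and it is the main reason the point is minor. What remains missing is a stated rule that these subjects count as failures, and a planned interval for the resulting rate.

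A third argument is that the failure rule needs a component with available data. If the position item is left blank for an abandoned procedure, the same rule gives a missing outcome. The documents do not say how the item is completed in that case. This stands in part: the absence of echo data does not force the exclusion, but the classification should be written down and not inferred.

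Finally, an attempt can begin with anesthesia or a monitoring line, so a per-attempt rate would count some cancellations unrelated to the device as failures. That is also true. It argues for showing both rates with reasons listed, and against replacing one by the other.

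**Conclusion.** The concern holds as a minor point. As written, the device success rate is conditional on full release of the valve, and subjects whom protocol 6.7 expressly provides for are left out of it. The rate per attempted procedure can only be equal or lower. For assumed success of 80-100% among 75 implanted subjects, the gap is 1.1-1.3 points with one such subject and 3.1-3.8 with three. With 50 implanted it is 1.6-2.0 and 4.5-5.7. With none it is zero.

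All of these sizes rest on assumed values of p and k, and on counting each never-released subject as a failure. No hypothesis test or success threshold in either document depends on this rate. The case for acting is that the second objective uses these rates for pivotal planning and that the classification is best settled before data are seen.

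**What to change.** In SAP 7.9.2.1, keep the Implanted-set rate as planned and add a supportive device success rate in the Attempted Implant set with its exact 95% interval. State that a subject with no study valve released counts as a failure on the positioning component, whether or not the position item was completed. Add a listing of the reason for each attempted procedure without an implant. Protocol 10.5 need not change, because SAP 7.1.3 already labels analyses in non-primary sets as supportive.

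The cost is two sentences and one listing. Attempt, release, position and death data are already collected. One item needs confirming: the reason field described in protocol 13.7 refers to implantation that was not attempted, and it is not stated whether it also covers procedures attempted without release. If it does not, the CRF guidance will need a small clarification. The added figure will be slightly less favorable whenever such a case occurs, and it will include some non-device cancellations, which the listing makes visible.

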7.9.2.2 Cardiovascular and heart failure hospitalizations at 30 days and 6 months

Cardiovascular and heart failure hospitalization will be adjudicated by the CEC and analysis will be based on data collected on the CEC adjudication form. The endpoint will be analyzed with Kaplan-Meier survival analysis according to Section 7.2 for each time point. Analysis of the endpoint will use the Attempted Implant set.

7.9.2.3 Heart failure events at 30 days and 6 months

Heart failure events will be adjudicated by the CEC and analysis will be based on data collected on the CEC adjudication form. The endpoint will be analyzed with Kaplan-Meier survival analysis according to Section 7.2 for each time point. The primary analysis will use the Attempted Implant set.

7.9.2.4 Hemodynamic performance metrics by Doppler echocardiography at discharge, 30 days, and 6 months

The following hemodynamic performance metrics by Doppler echocardiography will be reported at discharge, 30 days, and 6 months:

- Mean aortic gradient
- Effective orifice area
- Degree of total, para, and transvalvular prosthetic regurgitation
- Incidence of moderate and severe patient-prosthesis mismatch (PPM)

Endpoint Definitions:

Mean aortic gradient will be reported in units of mmHg.

Effective Orifice Area (EOA) in cm² will be derived according to the following formula

$$EOA = LVOT\ diameter^2 \times 0.785 \times (LVOT\ VTI / Aortic\ valve\ VTI)$$

Where: LVOT VTI is the velocity time integral of the left ventricular outflow tract in cm, and aortic valve VTI is the velocity time integral of the aortic prosthesis in cm.

Degree of total, para, and transvalvular prosthetic regurgitation will be reported in categories of none, trace, mild, moderate, and severe.

Patient-prosthesis mismatch (PPM)⁽¹⁾ is defined as follows:

For subjects with body mass index (BMI) < 30 kg/cm²

- **Moderate PPM:** EOAI = 0.85 – 0.65
- **Severe PPM:** EOAI < 0.65

For subjects with BMI ≥ 30 kg/cm²

- **Moderate PPM:** EOAI = 0.70 – 0.60
- **Severe PPM:** EOAI < 0.60.

Note that in the above, Effective Orifice Area Index (EOAI) in cm²/m² is defined as EOAI = EOA/BSA where EOA is the effective orifice area in cm² and BSA is the body surface area in m².

Analysis Methods:

Data for all endpoints will be reported on the core lab echo CRF. Mean aortic gradient and EOA will be summarized descriptively as continuous outcomes at each time point. Change from baseline in mean aortic gradient and EOA will also be summarized descriptively along with two-sided 95% confidence interval and p-value from a paired t-test. The degree of total, para, and transvalvular prosthetic regurgitation and incidence of moderate and severe PPM will be summarized with frequency counts and percentages at each follow-up time point. Analysis of each hemodynamic performance outcome will use the Implanted set.

7.9.2.5 Change from baseline in New York Heart Association (NYHA) functional classification at 30 days and 6 months

New York Heart Association (NYHA) functional classification will be reported on the follow-up CRF by the investigator as Class I, II, III, or IV. NYHA class will be summarized with frequency counts and

percentages for each follow-up time point. At each follow-up time point, change in NYHA class from baseline will be reported descriptively both as categorical and continuous variable. Categorical summary of change will include a summary of subjects with change of 3, 2, 1, 0, -1, -2, and -3 as well as a summary of improved, no change, worsened, or died. Continuous change from baseline will be summarized descriptively along with two-sided 95% confidence interval and p-value from a paired t-test. Analysis of the endpoint will use the Attempted Implant set.

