- Grade of diastolic dysfunction
- Pattern of LV geometry
- Peak average left ventricular global longitudinal strain (GLS) measured at end systole (aortic valve closure)
- Vendor, model, and software version of echocardiography system
- Tricuspid annular plane systolic excursion (TAPSE)
- Basal right ventricular linear dimension at end diastole (RVD)
- Right ventricular area at end diastole (RVAD)
- Right ventricular area at end systole (RVAS)

In addition, the following variables will be derived by the central database from the appropriate measurements reported by both the site and ECL.

- **Body Surface Area (BSA) in m²**
BSA = $0.007184 \times \text{height} \times \text{weight} \times 0.425$
Where: BSA is the body surface area in cm², height is in cm, and weight is in kg⁸
- **Body Mass Index (BMI) in kg/cm**
BMI = weight in kg/height in cm
- **Aortic Valve Area (AVA) in cm²**
AVA = LVOT diameter in cm² x 0.785 x (LVOT VTI/aortic valve VTI)
Where: LVOT VTI is the velocity time integral of the left ventricular outflow tract in cm, and aortic valve VTI is the velocity time integral of the native aortic valve in cm
- **Aortic Valve Area Index (AVAI) in cm²/m²**
AVAI = AVA/BSA
Where: AVA is the native aortic valve area in cm², and BSA is the body surface area in m²
- **Effective Orifice Area (EOA) in cm²**
EOA = LVOT diameter² x 0.785 x (LVOT VTI/Aortic valve VTI)
Where: LVOT VTI is the velocity time integral of the left ventricular outflow tract in cm, and aortic valve VTI is the velocity time integral of the aortic prosthesis in cm
- **Effective Orifice Area Index (EOAI) in cm²/m²**
EOAI = EOA/BSA
Where: EOA is the effective orifice area in cm², and BSA is the body surface area in m²
- **Doppler Velocity Index (DVI)**
DVI = LVOT VTI/Aortic valve VTI
Where: LVOT VTI is the velocity time integral of the left ventricular outflow tract in cm, and aortic valve VTI is the time velocity integral of the prosthetic aortic valve in cm

⁸ Height will be pulled from the site baseline eCRF, and weight will be pulled from the site eCRF for the visit

- **Estimated Right Ventricular Systolic Pressure (RVSP) in mmHg**
 $RVSP = (4 \times MVTR \text{ jet}^2) + 10$
Where: MV TR jet is the max velocity of the tricuspid regurgitant jet, and 10 = the assumed mean right atrial pressure in mmHg
- **Cardiac Output (CO) in l/min**
 $CO = (SV \times HR)/1000$
Where: SV is the stroke volume in ml/beat, and HR is the heart rate in beats per minute
- **Cardiac Index (CI) in l/min/m²**

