 $CI = CO/BSA$
Where CO is the cardiac output in l/min and BSA is Body Surface Area in cm²
- **Stroke Volume (SV) in ml/beat**
 $SV = LVOT \text{ diameter}^2 \times 0.785 \times LVOT \text{ VTI}$
Where: LVOT VTI is the velocity time integral from the left ventricular outflow tract in cm
- **Stroke Volume Index (SVI) in ml/beat/m²**
 $SVI = SV/BSA$
Where SV is stroke volume in ml/beat and BSA is Body Surface Area in m²
- **Stroke Volume RVOT (SV RVOT) in ml/beat**
 $SV \text{ RVOT} = RVOT \text{ diameter} \times RVOT \text{ VTI}$
Where RVOT diameter is the right ventricular outflow tract diameter in cm and RVOT VTI is the right ventricular velocity time integral
- **Aortic Regurgitant Volume (ARVol) in ml/beat**
 $RV = SV - SV \text{ RVOT}$
Where: $SV = LVOT \text{ diameter}^2 \times 0.785 \times LVOT \text{ VTI}$, and $SV \text{ RVOT} = RVOT \text{ diameter}^2 \times 0.785 \times RVOT \text{ VTI}$
- **Aortic Regurgitant Fraction (ARF) in %**
 $ARF = ARVol/SV$
Where ARVol is the aortic regurgitant volume in ml and SV is the stroke volume in ml
- **Left Atrial Volume Index (LAVI)**
 $LAVI = LAV/BSA$,
Where LAV is left atrial volume (biplane Simpson's) at end systole in ml, and BSA is body surface area in m²
- **Aortic transvalvular flow rate (AFR) in ml/second**
 $AFR = SV/ET$
Where SV is the stroke volume in ml/beat and ET is systolic ejection time in milliseconds
- **Valvulo-arterial impedance (Z_{va})**
 $Z_{va} = (MG + SAP)/SVI$
Where MG is mean aortic gradient in mmHg, SAP is systolic blood pressure in mmHg⁹, and SVI is stroke volume index in ml/beat/m² body surface area

⁹ Systolic blood pressure will be pulled from the site eCRF

- **E:e'**
Mitral inflow early (E) velocity/(mitral annular early (e') diastolic velocity; lateral + mitral annular early (e') diastolic velocity; medial)/2
- **E:A Ratio**
Mitral inflow early (E) velocity/ mitral inflow atrial (A) velocity
- **Left ventricular ejection fraction (LVEF) by modified-Simpson's rule**
$$\text{LVEF} = \frac{\text{LVEDV} - \text{LVESV}}{\text{LVEDV}} \times 100$$

Where LVEDV is left ventricular end-diastolic volume in ml and LVESV is left ventricular end systolic volume
- **Fractional Shortening (FS) in %**
$$\text{FS} = \frac{\text{LVIDD} - \text{LVIDS}}{\text{LVIDD}} \times 100$$

Where: LVIDD is left ventricular internal dimension at end diastole in cm, and LVIDS is left ventricular internal dimension at end systole in cm
- **Relative wall thickness (RWT)**

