 - Invasive diagnostic evidence with right heart catheterization showing a pulmonary capillary wedge pressure (pulmonary artery occlusion pressure) \geq 18 mmHg, central venous pressure \geq 12 mmHg, or a cardiac index < 2.2 L/min/m²
- 4) The patient receives at least one of the following treatments specifically for HF:
 - Initiation of intravenous diuretic or vasoactive agent (e.g. inotrope, vasopressor, or vasodilator)
Note that signification augmentation of oral diuretic therapy will not be sufficient to fulfill the urgent HF visit criteria
 - Mechanical or surgical intervention, including:
 - Mechanical circulatory support (e.g. intra-aortic balloon pump, ventricular assist device, extracorporeal membrane oxygenation, total artificial heart)
 - Mechanical fluid removal (e.g. ultrafiltration, hemofiltration, dialysis)

*Note that clinic visits for scheduled administration of HF therapies or procedures (e.g. intravenous diuretics, intravenous vasoactive agents, or mechanical fluid removal) **do not** qualify as non-hospitalized HF events.*

Device Success⁶³

All of the following:

- Absence of procedural mortality, **AND**
- Correct positioning of a single prosthetic heart valve into the proper anatomical location, **AND**
- Absence of patient prosthesis-mismatch and mean aortic valve gradient < 20 mmHg (or peak velocity < 3 m/sec), **AND**
- Absence of moderate or severe prosthetic valve regurgitation.

Bioprosthetic Valve Dysfunction (BVD)⁶³: Any of the following

- **Stenosis: moderate/severe**; any of the following:
 - Peak aortic velocity > 4 m/s OR mean aortic gradient > 40 mmHg, AND EOA < 0.8 cm²
 - Peak aortic velocity > 4 m/s OR mean aortic gradient > 40 mmHg, AND EOA ≥ 0.8 cm², **AND** DVI < 0.25
 - Peak aortic velocity ≤ 4 m/s and mean aortic gradient ≤ 40 mmHg, AND EOA < 0.8 cm², **AND** DVI < 0.25
- **Paravalvular regurgitation: moderate**
- **Paravalvular regurgitation: severe**
- **Transvalvular regurgitation: moderate**
- **Transvalvular regurgitation: severe**
- **Total regurgitation: moderate**
- **Total regurgitation: severe**

Notes:

1. For subjects with BSA < 1.6 m², the EOA criteria for significant (moderate or severe) stenosis is < 0.6 cm²
2. For subjects with LVOT diameter > 2.5 cm, the DVI criteria for significant (moderate or severe) stenosis is < 0.2
3. Reporting of prosthetic valve dysfunction will be based on core lab results.

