4. Bioprosthetic valve dysfunction events are not reported as adverse events, unless the dysfunction is accompanied with clinical sequelae at the time of event detection, and the clinical sequelae are chronologically and physiologically associated with the dysfunction. However, prosthetic dysfunctions that are associated with adverse events, and that meet the definition of a serious adverse event, should be reported as such.

Patient-Prosthesis Mismatch (PPM)⁶³

For subjects with BMI < 30 kg/cm²

- **Moderate PPM**: EOAI = 0.85 – 0.65
- **Severe PPM**: EOAI < 0.65

For subjects with BMI ≥ 30 kg/cm²

- **Moderate PPM¹²**: EOAI = 0.70 – 0.60
- **Severe PPM**: EOAI < 0.60

Bioprosthetic Valve Failure (BVF)⁹⁰: Any of the following:

- Autopsy findings of bioprosthetic valve dysfunction, likely related to the cause of death, or valve-related death (i.e. any death caused by bioprosthetic valve dysfunction or sudden unexplained death following diagnosis of bioprosthetic valve dysfunction)
- Repeat intervention (i.e. valve-in-valve TAVI, paravalvular leak closure or SAVR following confirmed diagnosis of bioprosthetic valve dysfunction)
- Severe bioprosthetic valve dysfunction

¹² Original VARC-2 definition lists 0.90-0.60 as moderate PPM range, this definition has been updated to reflect corrected range of 0.70-0.60 for moderate PPM

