2.0	
 Document updated throughout to align with the removal of Cohort A (Moderate Symptomatic AS) in protocol revision D Updated Kaplan-Meier standard error to use Greenwood’s method Remove required summary of domain scores for the efficacy endpoint change in KCCQ Removal of “Additional details have been detailed in the SAP for the planned subgroup analyses (Section 7.9.4) including identification of the endpoints to be analyzed as well as the addition of subgroup analysis based on NT-proBNP which was identified as clinically important” from Section 7.11 as the details in this document align with the subgroup analyses as specified in CIP revision D Added Section 9 (References) 	[name], Principal Statistician

2. List of Abbreviations and Definitions of Terms

Abbreviation	Definition
AE	Adverse event
AS	Aortic stenosis
BMI	Body mass index
BSA	Body surface area
BVD	Bioprosthetic valve dysfunction
BVF	Bioprosthetic valve failure
CEC	Clinical Events Committee
CIP	Clinical Investigation Plan
CRF	Case Report Form
DCS	Delivery catheter system
DVI	Doppler velocity index
E	Early diastolic mitral inflow velocity
e’	E prime; mitral annular early diastolic velocity

Abbreviation	Definition
E:e'	Ratio of early (E) mitral inflow velocity to early (e') mitral annular velocity
EOA	Effective orifice area index
EOAI	Effective orifice area index
GLS	Global longitudinal strain
KCCQ	Kansas City Cardiomyopathy Quality of Life
LVEF	Left ventricular ejection fraction
LVOT	Left ventricular outflow tract
NT-proBNP	N-terminal pro B-type natriuretic peptide
NYHA	New York Heart Association
PPM	Patient-prosthesis mismatch
PPI	Permanent pacemaker implant
QoL	Quality of Life
SAE	Serious adverse event
SAP	Statistical Analysis Plan
SVI	Stroke volume index
TAV	Transcatheter aortic valve
TAVR	Transcatheter aortic valve replacement
TEE	Transesophageal echocardiography
VARC-2	Valve Academic Research Consortium
VTI	Velocity time integral
6MWT	Six-minute walk test

3. Introduction

This Statistical Analysis Plan (SAP) has been designed to document, before data are analyzed, the rationale for the study design, and the planned analyses that will be included in study reports and study-specific publications for the Evolut™ EXPAND TAVR I Feasibility Study. This version of the analysis plan was developed under the approved Clinical Investigation Plan (CIP) and approved Case Report Form (CRF) Requirements.

4. Study Objectives

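### As printed, the PPM cut-off at BMI 30 kg/cm² can never be reached, and the endocarditis criteria give four combinations both a definite and a possible code

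*SAP*

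**What the plan says.** **PPM.** SAP 7.9.2.4 and Protocol 13.8.3 give the same limits. Below the BMI cut-off, moderate PPM is EOAI 0.65 to 0.85 and severe is below 0.65. The second set applies "For subjects with BMI ≥ 30 kg/cm²": moderate is 0.60 to 0.70 and severe is below 0.60. Both documents print the unit as kg/cm² on both lines. A protocol footnote shows that the upper-BMI range was deliberately revised: "this definition has been updated to reflect corrected range of 0.70-0.60 for moderate PPM". Device success (SAP 7.9.2.1) requires that PPM be absent at discharge and points to the same rule: "Patient prosthesis mismatch is defined in Section 7.9.2.4".

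**Endocarditis.** Protocol 13.8.2 lists the routes to definite prosthetic valve endocarditis by clinical criteria: two major; one major or three minor; five minor. A note after the minor criteria then codes a case with only one major and one or two minor, or with only three or four minor, as possible. SAP 7.9.3 gives no definition. It analyses the outcome (additional outcome measure 10) by Kaplan-Meier from CEC adjudications.

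**E:e'.** Protocol 13.3.5 gives the derivation as "Mitral inflow early (E) velocity/(mitral annular early (e') diastolic velocity; lateral + mitral annular early (e') diastolic velocity; medial)/2". The SAP abbreviation list describes E:e' as "Ratio of early (E) mitral inflow velocity to early (e') mitral annular velocity", and SAP 7.9.2.10 has no formula.

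**The concern.** The first two are rules that decide a subject's category, and each is wrong or contradictory on the page.

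The PPM rule feeds two efficacy endpoints: the incidence of moderate and severe PPM and, through 7.9.2.1, device success. If the unit were programmed as printed, the range that the footnote sets out to correct would apply to nobody.

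The endocarditis rule lets two adjudicators code the same case differently while both follow the protocol. Checks on programming cannot detect that, because the ambiguity enters at adjudication.

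The study exists to supply estimates for pivotal design, so category counts and rates are its product. The E:e' line is a lesser matter of notation, but it concerns a key efficacy endpoint.

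**Working it through.** The plan states no figure to reproduce here, so the check applies each rule as printed.

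**1. PPM unit.** Inputs: the cut-off of 30 kg/cm² and the EOAI limits, from SAP 7.9.2.4. Body size is my illustration.
- 95 kg at 170 cm: 95/1.70² = 32.9 kg/m², but 95/170² = 0.0033 kg/cm².
- Weight needed at 170 cm: 30 × 170² = 867,000 kg.
- Extreme case, 200 kg at 140 cm: 200/140² = 0.0102 kg/cm².

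The upper-BMI branch is therefore empty. For a subject at or above 30 kg/m²:

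| EOAI | As printed | With kg/m² |
|---|---|---|
| below 0.60 | severe | severe |
| 0.60 to below 0.65 | severe | moderate |
| 0.65 to 0.70 | moderate | moderate |
| above 0.70 to 0.85 | moderate | none |
| above 0.85 | none | none |

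Only the fourth row can change device success, since any PPM is a failure. The second row changes PPM severity alone. One subject moved is 1/75 = 1.3 points if all 75 are evaluable, or 1/50 = 2.0 points at an initial analysis of 50. It is slightly more if fewer are evaluable, because SAP 7.9.2.1 counts only subjects with known status.

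**2. Endocarditis.** I took every combination of 0 to 2 major and 0 to 6 minor criteria (3 × 7 = 21) and applied both passages.

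| Major, minor | Definite list | Later note |
|---|---|---|
| 1, 1 | definite | possible |
| 1, 2 | definite | possible |
| 0, 3 | definite | possible |
| 0, 4 | definite | possible |

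These four are all the combinations that the note covers, so the possible code never applies alone. One major criterion with no minor ones is also definite. The two-major and five-minor routes add nothing, because any such case already has at least one major or three minor criteria. If the middle route required both counts together, the overlap would fall to none, and the other two routes would add five combinations: (2,0), (2,1), (2,2), (0,5) and (0,6). That suggests where the slip lies; it does not settle which text the CEC has used.

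**3. E:e'.** By ordinary operator order the printed line is E/(l + m)/2, where l and m are lateral and medial e'. The evident intent is E/[(l + m)/2]. Their ratio is [E/(2(l + m))] / [2E/(l + m)] = 1/4 for any values. With E = 80 and e' of 9 and 7 cm/s, the line gives 80/16/2 = 2.5, against 80/8 = 10.0. A mean change of -2.0 would appear as -0.5. Standard deviation and confidence limits shrink by the same factor; the paired t-test p-value and the direction do not change.

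**The case against.** The strongest reply is that these are drafting slips with an obvious meaning. Anyone who programmed the PPM rule would see an empty branch. SAP section 8 requires independent validation of all efficacy endpoints, and both PPM definitions cite their source document, so a validator has something to check against. This stands. It removes any claim that the error must reach the results or that no correct rule is available. It does not make the printed unit right, and the superscript is intact in both documents.

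On endocarditis, the outcome is an additional measure, adjudicated by independent physicians under a charter that is not among the documents. The SAP does not say whether possible cases count as events. So no effect on an estimate can be shown, but the contradiction between the two passages remains.

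The objection is strongest on E:e'. Bracketing the sum before dividing by two plainly signals a mean. The layout of that line may not have survived in the text, and quarter-scale values would stand out against the E/e' levels of 15 and 12 in the heart failure definitions of Protocol 13.8.3. It is a missing bracket, and does not rank with the other two.

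A reader might also infer from Protocol 13.3.5 that the BMI and BSA formulas are wrong and that every indexed variable is therefore unsafe. The documents do not support that. Exponents may have been lost from both lines in the text. Only a label conflict is clear: the BSA heading gives m², while the explanatory line says "BSA is the body surface area in cm², height is in cm, and weight is in kg". The m² scale is used elsewhere, for example "For subjects with BSA < 1.6 m², the EOA criteria for significant (moderate or severe) stenosis is < 0.6 cm²".

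**Conclusion.** The point holds for two definitions. The PPM cut-off is stated in a unit that leaves the upper-BMI branch empty, and the endocarditis passages give four combinations two codes each. Both should be corrected, because they are wrong or contradictory as stated rules and not merely short of detail. Confidence is high about the text and does not extend to any realised error.

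The PPM consequence arises only if the unit was programmed literally. It then affects only subjects at or above 30 kg/m² whose EOAI lies in one of the two bands. The documents do not allow that number to be estimated, and it may be zero. The same is true of endocarditis cases.

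It would be tempting to conclude that device success will be understated, or that E:e' results will be a quarter of their true size. Neither follows: the database specification and case report forms are not among the documents, and the intended meaning is plain in both cases. E:e' is a clarification only.

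**What to change.** - **SAP 7.9.2.4 and Protocol 13.8.3:** state the PPM cut-off as 30 kg/m² on both BMI lines. Confirm that PPM was programmed that way, and re-derive PPM and device success only if it was not.
- **Protocol 13.8.2:** reconcile the definite list with the note on possible cases so that each combination has one code. Align the CEC's working definition and recheck any case already adjudicated. The choice of wording belongs to the sponsor and the CEC.
- **Protocol 13.3.5, clarifications:** write E:e' as E/[(lateral e' + medial e')/2] and confirm the database derivation. It would help to repeat the formula in SAP 7.9.2.10. Align the BSA unit label with the m² of its heading.

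The cost is a few lines of wording in two documents, a check of existing programs and a review of any adjudicated endocarditis cases. No new data are needed.
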